5.3.1.4. Acceptability and Palatability of the JNJ-53718678 formulation

Formula to be used for acceptability and palatability parameter is provided in [Table 21](#).

Table 21: Acceptability and Palatability Parameter

Measurement	Formula
Acceptability and palatability [categorical]	
Assessment of 'In general, how did the child react when he/she was given the medicine? (note all that apply)'
 
 Child took medicine easily  Disgusted expressions after tasting medicine  Cried after tasting medicine  Would not open mouth or turned head away to avoid medicine  Spit out or coughed out medicine  Gagged  Vomited (within 2 minutes of swallowing medicine)
 
This is only captured once during visit Day 8

Acceptability and palatability [binary]	
Assessment of 'In general, how did the child react when he/she was given the medicine? (note all that apply)'
 
Categorized as 'Acceptable' (1) if answered:  Child took medicine easily
 
Categorized as 'Partly or Not Acceptable' (0) in case any of the following responses were entered by the caregiver:
 
 Disgusted expressions after tasting medicine  Cried after tasting medicine  Would not open mouth or turned head away to avoid medicine  Spit out or coughed out medicine  Gagged  Vomited (within 2 minutes of swallowing medicine)
 
This is only captured once during visit Day 8

5.3.1.5. Medical Resource Utilization

Medical resource utilization will be assessed by the number, frequency and type of medical care encounters, including for RSV infection or RSV-related complications, based on investigator assessment.

Summary information will be provided as follows:

- Number of medical care encounters and reason (AE, Other)
- Type of medical care encounters such as medical practitioner office, emergency room, intensive care unit, home care, amongst others
- Type of practitioner
- Frequency of visits

5.3.2. Endpoint-specific analysis methods

5.3.2.1. RSV RNA Viral Load (qRT-PCR)

Log₁₀ RSV RNA Viral Load

Descriptive statistics mean (SE) graphs and median (IQR) graphs will be shown for the log₁₀ RSV RNA viral load actual values and changes from baseline by analysis visit and by treatment group. Descriptive statistics will include the number of subjects, mean, standard deviation, standard error, 95% confidence interval, median, range and interquartile range. The aforementioned will be presented by the subgroups as defined in Section 2.4.

Differences on log₁₀ RSV RNA viral load by qRT-PCR between treatment groups and by analysis visit will be determined using appropriate contrasts in a similar mixed effects model as the one used for the primary efficacy endpoint (see Section 5.2.3). The 95% 2-sided confidence intervals will be presented.

Association Between Log₁₀ RSV RNA Viral Load and Covariates/Baseline Indicators

The potential association between the log₁₀ RSV RNA viral load and the following covariates and/or baseline indicators will be explored:

- Baseline log₁₀ RSV RNA viral load
- Presence/absence of risk factors for severe RSV disease
- Days since symptom onset (0,1,2,3,4,5)
- RSV subtype
- Medications of interest:
 - ◆ Any prior/concomitant use
 - ◆ No prior/concomitant use
- Supplemental oxygen at baseline
- Presence of other respiratory pathogens at baseline
- Presence of other respiratory viruses at baseline
- Age as collected at Screening (as continuous variable)
- Overall RSV symptoms summary score (ObsRO) at baseline
- Overall RSV symptoms summary score (ClinRO) at baseline
- Region [Class 2]
- Cohort [Class 1]
- Baseline neutrophils count (as continuous variable)

To predict the change in log₁₀ RSV RNA viral load over time at Day 3, Day 5 and Day 8 based on the aforementioned set of predictor variables (covariates and/or baseline indicators), multiple regression analysis using backward stepwise elimination, will be performed initially fitting all predictor variables to identify the prognostic factors. Then

factors are deleted one-by-one until a stopping condition is satisfied. At each step, the factor showing the smallest contribution to the model is eliminated. The parameter estimates along with the 95% 2-sided confidence limits by predictor variable will be produced. In addition, residual plots and goodness of fit measures will be evaluated, but not displayed in output. The SAS® procedure GLM SELECT (selection = backward SLS = 0.1) will be used. The procedure removes factors based on significance level and stops when all factors in the model are significant at the 0.1 level.

Predictor variables which show a strong association may further be explored as additional covariates in the primary efficacy model described in Section [5.2.3](#).

RSV RNA Viral Load AUC

A similar model as used for the primary analysis will be used for the RSV RNA viral load AUC until Day 3 and until Day 8. The differences in these AUCs for active versus placebo will be derived using appropriate contrasts for both Day 3 and Day 8 and from the same model containing all RSV RNA viral load assessments from baseline through Day 8.

Least squares mean estimates of the treatment differences, including the 95% 2-sided confidence intervals, will be presented.

For subgroup analyses, the model will also include subgroup variable as covariate, subgroup-by-treatment, subgroup-by-analysis visit and subgroup-by-analysis visit-by-treatment interactions. For details about subgroups refer to Section [2.4](#).

The individual AUCs until Day 14, derived using the trapezoidal method, will be analyzed using a generalized linear model with $AUC_{Day14/0-312h}$ as a dependent variable, treatment group and randomization stratification factors (derived) as fixed factors, and baseline \log_{10} RSV RNA viral load as fixed covariate. The differences versus placebo will be estimated using appropriate contrasts and presented with 95% 2-sided confidence intervals.

Proportion of Subjects with Undetectable RSV RNA Viral Load

The proportion of subjects within the RSV RNA viral load categories (undetectable, detectable and quantifiable) will be shown in a frequency tabulation, as well as graphically, by treatment group and analysis visit. Subjects with missing data at that analysis visit will not be counted in the denominator for the proportion. Additionally, 95% 2-sided confidence interval for each binomial proportion within the individual categories will be presented as based on the Wilson score test.

Based on the binary categorization:

- Detectable or quantifiable = Yes (1)
- Undetectable = No (0)

the difference in proportion of undetectable between each active treatment group as compared to placebo will be investigated. Frequency procedure in SAS® provides Newcombe confidence limits with Mantel-Haenszel weights for the common risk difference, controlling for the two randomization stratification factors (separately). The

difference in proportion of undetectable and 95% 2-sided confidence interval for this point estimate, controlling for randomization stratification factors, will be presented.

The aforementioned will be presented overall by treatment group and by the subgroups as defined in Section 2.4.

Time to Virus Undetectable [time to event]

With reference to the two time to event approaches, their definitions and derivations detailed in Section [5.3.1.1](#):

The time to event variables will be analyzed using Kaplan-Meier analysis (for both approaches). A summary table including number of subjects included in the analysis, number of subjects censored, 25th and 75th percentiles and median time to event, with 95% 2-sided confidence intervals based on Kaplan-Meier transformation method, will be presented by treatment group. The data will be presented graphically using the Kaplan-Meier estimate of the survival function by treatment group.

The aforementioned will be presented overall by treatment group and by the subgroups as defined in Section 2.4, for time (hours) to **confirmed undetectable** viral load only.

As sensitivity analysis, overall summary tables will be presented as described above for time (hours) to **confirmed undetectable** viral load but excluding nasal swab samples as previously described (refer to Section [5.2.3](#)).

In addition to the Kaplan-Meier analysis, as described above, time (hours) to **confirmed undetectable** viral load and the differences in time to **confirmed undetectable** viral load of active dosing regimens versus placebo treatment, will also be estimated using the accelerated failure time (AFT) model, using the log-logistic distribution. The AFT model will include the categorical effects for treatment (with placebo as the reference), randomization stratification factors (derived) and baseline log₁₀ RSV RNA viral load as continuous covariate. A summary of information from the final AFT model will include parameter estimates and associated standard errors and covariance matrix of parameter estimates, estimated accelerated failure time ratios versus placebo and associated 95% 2-sided confidence intervals.

The aforementioned will be presented overall by treatment group and by the subgroups as defined in Section 2.4.

The parameter estimates and associated variance matrix resulting from AFT model, will be used in a generalized MCP-Mod approach that will test for existence of dose-response, at alpha=0.10 (1-sided). The aforementioned will be presented overall by treatment group only.

Graphical presentation will include:

- Overlay of survival curves with Kaplan-Meier survival function and AFT on one plot
- Forest plot of accelerated failure time ratios and resulting confidence intervals for subgroups of interest as defined in Section 2.4 including the relevant subgroup variable as covariate in the model with subgroup*treatment group interaction.

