1.2. Trial Design

This is a Phase 2 multicenter, double-blind, placebo-controlled, randomized study to evaluate the antiviral activity, clinical outcomes, safety, tolerability, and PK/PD relationships of different oral dose levels of JNJ-53718678 in children ≥ 28 days and ≤ 3 years of age with RSV disease (hospitalized subjects [Cohort 1] or outpatients [Cohort 2]).

Up to 4 IAs are planned for this study. For the full trial design please refer to Section 3.1 of the protocol.

The total number of subjects is planned to be approximately 294 (approximately 144 in Cohort 1 and approximately 150 in Cohort 2; approximately 196 subjects receiving JNJ-53718678 and approximately 98 subjects receiving placebo). The sample size of Cohort 2 may be re-estimated to a maximum of 300 in Cohort 2 based upon results from the third IA.

Overall, for both cohorts, the study will include a Screening Period (Day -1 to Day 1), a Treatment Period (Day 1 to Day 8), and a Follow-up Period (Day 9 to Day 28 [± 3]). The total study duration for each subject will be approximately 29 days (Screening included). A diagram of the study design is provided in [Figure 1](#).

Figure 1: Schematic Overview of the Design of Study 53718678RSV2002

a) Cohort 1 after discharge and Cohort 2.

b) Subjects can be discharged as of Day 2.

c) A subcohort of 6 subjects >2 and ≤3 years included in Cohort 1 will be included ([low dose JNJ-53718678 [N=2], high dose JNJ-53718678 [N=2], and placebo [N=2]]). While this subcohort is ongoing, additional subjects >2 and ≤3 years of age are not allowed to be enrolled in the Cohort 2.

d) In case of ongoing AE(s).

e) The study will start with Cohort 1 (including the subcohort). After the first interim analysis an IDMC will review the interim data, and will issue its recommendation to the sponsor, based on which the Sponsor Committee will decide whether to initiate enrollment in Cohort 2, while hospitalized subjects continue to be enrolled.

f) Sample size of Cohort 2 might be re-estimated to a maximum of N=300.

Note: Age group 1: ≥28 days and <3 months of age; Age group 2: ≥3 months and <6 months; Age group 3: ≥6 months and ≤3 years

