The potential association between the change from baseline in summary scores of the summary parameter, PRESORS ObsRO: key RSV symptoms and the covariates and/or baseline indicators of interest will be explored over time at Day X, Day 8 and Day 10 in a similar manner, utilizing multiple regression with backward stepwise elimination, as described for the RSV RNA viral load. Refer to Section [5.3.2.1](#) for details.

Day X is defined as the day when at least 50% of Cohort 1 subjects, across all treatment groups, have been discharged from hospital. The day identified will be used for both cohorts.

PRESORS ObsRO: Change from Baseline: Mixed Model Repeated Measures

For the summary parameter, PRESORS ObsRO: key RSV symptoms, change from baseline over time (average of the worst [primary approach] daily summary scores) will be analyzed using a restricted maximum likelihood based repeated measures approach. The analysis model will include fixed (discrete) effect parameters for treatment, randomization stratification factors (derived), analysis visit and treatment-by-analysis visit interaction, as well as continuous covariates for the baseline summary parameter score and baseline summary parameter score-by-analysis visit interaction. An unstructured covariance structure will be selected to model the within-subject errors. In case this model will not converge, the Toeplitz covariance structure will be applied. The Kenward-Roger approximation will be used to estimate the denominator degrees of freedom.

Differences between treatment groups and by analysis visit will be determined using appropriate contrasts. Both the 80% and 95% 2-sided confidence intervals will be presented.

For subgroup analyses, the model will also include the subgroup variable as a covariate and the subgroup-by-treatment, subgroup-by-analysis visit and subgroup-by-analysis visit-by-treatment interactions. For details about subgroups refer to Section [2.4](#).

Time to Resolution of Symptoms (Concepts) and Four Summary Parameters: Key RSV Symptoms, Respiratory Symptoms, General Illness Behavior and Overall RSV Symptoms (ObsRO)

For the RSV symptoms (concepts) and four summary parameters, these time to event variables will be analyzed using Kaplan-Meier analysis. Both the 80% and 95% 2-sided confidence intervals will be presented.

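### Backward elimination at the 0.1 level over 14 candidates keeps a noise factor in about 75% of runs, and 95% limits taken from the selected model cover only about half the time for such factors

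*SAP*

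**What the plan says.** The part of SAP section 5.3.2.1 on associations with covariates and baseline indicators lists 14 candidates: baseline viral load, risk factors, days since onset, subtype, medications of interest, oxygen at baseline, other pathogens, other viruses, age, the ObsRO and ClinRO overall scores, region, cohort and neutrophil count.

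The aim is stated as "To predict the change in log₁₀ RSV RNA viral load over time at Day 3, Day 5 and Day 8". The regression "will be performed initially fitting all predictor variables to identify the prognostic factors". Software and threshold are fixed: "The SAS® procedure GLM SELECT (selection = backward SLS = 0.1) will be used". The stopping rule is "The procedure removes factors based on significance level and stops when all factors in the model are significant at the 0.1 level". On reporting, the section says "The parameter estimates along with the 95% 2-sided confidence limits by predictor variable will be produced". It does not name the model that supplies these limits, and it mentions no shrinkage, resampling or caveat. A closing sentence allows strongly associated predictors to be explored as extra covariates in the primary model.

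Section 5.3.2.2 applies the method to change in the key RSV symptoms score at three times: Days 8 and 10, and a Day X set by when half of Cohort 1 has left hospital. Its description of the method is "in a similar manner, utilizing multiple regression with backward stepwise elimination, as described for the RSV RNA viral load".

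**The concern.** A noise factor reaches the final model only when its p-value is at or below 0.1. A 95% interval for it is therefore displayed only after a screen that favours estimates far from zero. The interval's label promises 95% coverage, and for these factors the screen removes that property.

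The impact of baseline characteristics on antiviral activity and clinical course is a secondary objective (section 1.1), and these regressions address it. A reader of the study report would see a short list described as prognostic, with limits that appear to carry their usual meaning. The risk is that chance factors are taken forward as real, with too much precision attached.

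**Working it through.** The SAP gives no false-selection rate or coverage for this procedure, so there is no figure to reproduce.

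**Inputs from the SAP:** 14 candidates, stay level 0.1 and unadjusted 95% limits (section 5.3.2.1). On sample size, section 1.2 says "The total number of subjects is planned to be approximately 294", of which about 144 are in Cohort 1 and 150 in Cohort 2. Section 5.1 asks for combined and by-cohort analyses.

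**Assumptions:** limits come from the selected model; each day is a separate run; correlations and prevalences among candidates are invented for the simulations, since the SAP gives none.

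**Step 1, at least one noise factor kept (independent candidates).**
- All 14 null: 1 − 0.9^14 = 77.1%.
- 13 null, baseline viral load truly prognostic: 1 − 0.9^13 = 74.6%.

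**Step 2, coverage for a retained single-df noise factor.** The 95% interval contains zero when p > 0.05, and the factor is shown only when p ≤ 0.10. Coverage is therefore (0.10 − 0.05)/0.10 = 50%.

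**Step 3, simulation of the elimination with partial F tests.**

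| Design | Any noise factor kept | Mean kept | Coverage, 1-df noise factors |
|---|---|---|---|
| n = 250, baseline viral load real | 75.4% | 1.36 | 46.9% |
| n = 144, 14 independent nulls | 78.5% | 1.52 | 47.0% |
| n = 294, 14 independent nulls | 78.0% | 1.46 | 48.6% |
| n = 144, correlated, baseline viral load real | 75.7% | 1.53 | 44.2% |
| n = 294, correlated, baseline viral load real | 74.3% | 1.39 | 44.9% |

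The correlated designs nest viruses within pathogens and oxygen use within cohort, correlate ObsRO with ClinRO, and give subtype 2 df and region 3 df. The rows shown enter days since onset as linear. With days as six classes and baseline viral load real, the retention rates are 74.3% (n = 144) and 76.6% (n = 294). A further rerun at n = 144 to 290 gave 74–77% retention, about 1.4 kept, and 46–50% coverage, against about 95% from the full model. The conclusion depends little on sample size or correlation; under the assumed correlations coverage falls slightly lower, to 42–46%.

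**Step 4, how many retained noise factors have limits that exclude zero.** 1.36 × (1 − 0.469) = 0.72, or about 0.7 per run.

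**Step 5, the same count under the full model.** 13 × 0.05 = 0.65 per run. Simulated means, elimination against full model, are 0.69 and 0.64 at n = 250, and 0.73 and 0.63 at n = 144. At least one such factor appears in 50% against 48% of runs at n = 250, and in 51% against 46% at n = 144.

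**Step 6, size of the full model.** Twelve single-df candidates plus 2 (subtype) plus 3 (region) make 17 df. Three treatment groups add 2, giving 19. Days since onset as six classes adds 4, giving 23. Cohort drops out of single-cohort runs. With 144 subjects and 22 df plus an intercept, 121 residual df remain.

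**The case against.** The strongest case is that this is a disclosed, reproducible screen in an exploratory analysis. Section 5.3.2.1 says the associations will be explored, and section 5.1.1 describes the study as exploratory. The regressions carry no alpha and appear in no futility, enrichment or sample-size rule in section 5.6. The primary covariates are fixed in section 5.2.3, and extra ones only may be explored. All of this stands, and it limits the importance of the point. Effect modification is handled separately, by subgroup-by-treatment interaction models without selection.

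It is also fair that the remedy hardly changes how many noise factors look significant at 5% (step 5), and that the SAP does not say the limits come from the selected model. If they already come from the full model, the coverage problem disappears and only the sentence needs clarifying.

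Four stronger readings are tempting but unsupported:
- *All of the roughly 1.4 retained noise factors look significant.* Only about 0.7 have limits that exclude zero. The rest have p between 0.05 and 0.10.
- *Six regressions yield about eight false factors.* 6 × 1.36 is about 8 factor-by-day retentions. Days share subjects and predictors, so one chance factor can be counted more than once.
- *The primary analysis is contaminated.* Nothing selected enters it as pre-specified.
- *Leaving treatment out of the list biases the results.* Randomization makes treatment independent of true baseline factors, so the omission mainly adds residual variance. Medications of interest also counts concomitant use and so is not purely baseline, but no effect of this has been quantified.

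**Conclusion.** The point holds as a fault in the reported limits. About 75% of runs keep at least one noise factor, with a mean of about 1.4 if only baseline viral load is truly prognostic. Limits taken from the selected model cover about 46–50% of the time for retained single-df noise factors, slightly less under the assumed correlations.

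The coverage figure does not apply to strong true predictors, and the 75% would be lower if more candidates were truly associated. A reader might infer that dropping elimination would remove most spurious findings. It would not: the count at the 5% level goes only from about 0.7 to about 0.65 per run. The gain is limits that mean what their label says, and no prognostic label for noise with p between 0.05 and 0.10. The correction is worth making because it is cheap and the analysis serves a stated secondary objective. No trial conclusion depends on it.

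**What to change.** Replace the reporting text in section 5.3.2.1 with, for example:

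> Estimates and 95% confidence limits are reported from the full model containing treatment group and all pre-listed predictors, without elimination. Backward elimination, if run, serves only to rank predictors; no 95% limits are attached to the selected model. Results are exploratory and are not adjusted for the number of predictors.

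State whether days since onset is linear or categorical, and make the same change in section 5.3.2.2.

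The change needs SAP wording and a simpler program. It needs no new data and leaves the primary analysis unchanged. The price is slightly wider intervals, a longer table and fewer residual degrees of freedom in the single-cohort runs of about 144 to 150 subjects. Overlapping candidates, such as other viruses within other pathogens, may have noticeably wider limits; that widening was not quantified.
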